#### **6.10.3.2. Incidence of SARS-CoV-2 Infection by Day 29**

As a key secondary endpoint, the proportion of patients in the Prevention populations who are SARS-CoV-2 positive postbaseline (Table PYAD.4.1) by Day 29 will be summarized by treatment group. Similar methodology, as described in Section 6.10.1 will be utilized for statistical hypothesis testing, following the testing scheme described in Section 6.5.

Results of SARS-CoV-2 tests during the study will be listed for each participant.

As a sensitivity analysis, the percentage of patients in the Prevention population who experience death or are SARS-CoV-2 positive postbaseline by Day 29 will be summarized by treatment group. Similar methodology, as described in Section 6.10.1 will be utilized for statistical hypothesis testing.

#### **6.10.3.3. SARS-CoV-2 Infection by Day 57**

The percentage of patients in the Prevention population who are SARS-CoV-2 positive postbaseline by Day 57 will be summarized by treatment group. Statistical comparison between each study intervention and placebo will be done using the logistic regression model described in Section 6.10.1.

#### **6.10.3.4. Hospitalization or Death Due to COVID-19 by Day 57**

The proportion of patients who experience hospitalization or death due to COVID-19 during the Evaluation Period will be summarized for participants in the Prevention population. In addition, the number of patients that experience hospitalization or death due to COVID-19 will be analyzed using logistic regression to compare each study intervention versus placebo, if there are sufficient data available. Statistical comparisons will be done using a logistic regression model. The model will include treatment, facility, role within the facility (resident vs staff) and sex as fixed effects. Missing data will be imputed using the NRI method as described in Section 6.3.3.

A listing of hospitalization status during the Evaluation Period will be created.

As an exploratory analysis, this analysis will be repeated on participants in the Treatment populations. Additionally, at each End of Evaluation Database Lock, the number of patients who are hospitalized or have died due to COVID-19 anytime after randomization will be analyzed to compare each study intervention versus placebo in the Prevention and Treatment populations, if there are sufficient data available.

#### 6.10.3.5. COVID-19-Related Deterioration (Hospitalization, Emergency Room, or Death by Day 57)

Proportion (percentage) of participants who experience deterioration by Day 57 will be analyzed and is defined as:

- COVID-19-related hospitalization (defined as  $\geq 24$  hours of acute care)
- a COVID-19-related emergency room visit, or
- death related to COVID-19

The proportion of patients that experience deterioration by Day 57 will be summarized by treatment group in frequency tables and listed for participants in the Prevention Population.

In addition, the number of patients that experience deterioration by Day 57 will be analyzed using logistic regression to compare each study intervention versus placebo, if there are sufficient data available. Statistical comparisons between each study intervention and placebo will be done using a logistic regression model. The model will include treatment, facility, role within the facility (resident vs staff) and sex as fixed effects. Missing data will be imputed using the NRI method as described in Section 6.3.3.

As an exploratory analysis, this analysis will be repeated on participants in the Treatment populations for events of deterioration up to the end of their respective Evaluation Periods.

#### 6.10.3.6. COVID-19-Related Mortality by Day 57

The proportion of patients that experience death due to COVID-19 by Day 57 will be summarized by treatment in frequency tables and listed for participants in the Prevention Populations.

In addition, the number of patients that experience death due to COVID-19 by Day 57 will be analyzed using logistic regression to compare each study intervention versus placebo, if there are sufficient data available. Statistical comparisons between each study intervention and placebo will be done using a logistic regression model. The model will include treatment, facility, role within the facility (resident vs staff) and sex as fixed effects. Missing data will be imputed using the NRI method as described in Section 6.3.3.

As an exploratory analysis, this analysis will be repeated on participants in the Treatment populations for deaths due to COVID-19 by the end of their respective Evaluation Periods.

Additionally, at each End of Evaluation Database Lock, the number of patients who experienced death due to COVID-19 anytime after randomization will be analyzed to compare each study intervention versus placebo in the Prevention and Treatment populations, if there are sufficient data available.

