Safety, pharmacokinetics, and antidrug antibodies will be characterized in the overall intent to treat population and in the analysis populations.

Additional population subset analyses are detailed in Section 9 and/or in the statistical analysis plan.

Prevention Population Objectives and Endpoints	
Participants negative at baseline for SARS-CoV-2 RT-PCR and serology	
Comparison Groups: Placebo vs LY3819253 4200 mg	
Objectives	Endpoints
Primary	

Compare the incidence of COVID-19	
Cumulative incidence of COVID-19 defined as the detection of SARS-CoV-2 by RT-PCR AND mild or worse disease severity^a within 21 days of detection
Time frame for endpoint evaluation: 8 weeks from randomization
Key Secondary	

Compare the incidence of moderate or worse severity COVID-19	
Cumulative incidence of moderate or worse severity COVID-19; defined as the detection of SARS-CoV-2 by RT-PCR AND moderate or worse disease severity^a within 21 days of detection
Time frame for endpoint evaluation: 8 weeks from randomization

Compare the incidence of SARS-CoV-2 infection	
Cumulative incidence of SARS-CoV-2; defined as the detection of SARS-CoV-2 by RT-PCR
Time frame for endpoint evaluation: 4 weeks from randomization

Other Secondary	
[time frame for endpoint evaluation: 8 weeks from randomization]	
• Compare the incidence of SARS-CoV-2 infection	• Cumulative incidence of SARS-CoV-2 infection defined as the detection of SARS-CoV-2 by RT-PCR
• Compare the frequency of hospitalization or death due to COVID-19	• Proportion of participants who are hospitalized or have died due to COVID-19
• Characterize clinical status for participants.	• Proportion (percentage) of participants who experience these events: ○ COVID-19 related hospitalization (defined as ≥ 24 hours of acute care), ○ COVID-19 related emergency room visit, or ○ death
• Compare the mortality due to COVID-19	• Proportion of participants who die due to COVID-19 (according to the investigator)

Abbreviations: COVID-19 = coronavirus disease – 2019; RT-PCR = reverse transcription – polymerase chain reaction; SARS-CoV-2 = severe acute respiratory syndrome coronavirus 2.

^a As defined in [Table 1](#).

Part 2 Prevention

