9.4. Statistical Analyses

Statistical analysis of this study will be the responsibility of Sponsor or its designee.

All tests of treatment effects will be conducted at a 2-sided alpha level of 0.05, unless otherwise stated, and all confidence intervals will be given at a 2-sided 95% level.

For subgroup analyses, all tests of interactions between treatment groups and other factors will be conducted at a 2-sided alpha level of 0.10.

Any change to the data analysis methods described in the protocol will require an amendment only if it changes a principal feature of the protocol. Any other change to the data analysis methods described in the protocol, and the justification for making the change, will be described in the statistical analysis plan (SAP) and the clinical study report (CSR). Additional exploratory analyses of the data will be conducted as deemed appropriate.

The statistical analysis plan will be finalized prior to un-blinding and it will include a more technical and detailed description of the statistical analyses described in this section. This section is a summary of the planned statistical analyses of the most important endpoints including primary and key secondary endpoints.

For analyses on the Part 2 Prevention population, LY3819253 700 mg and LY3819253 350 mg + LY3832479 700 mg will be assessed against placebo separately.

For analyses on the Part 3 Treatment population, results will be summarized separately for LY3819253 700 mg and LY3819253 700 mg + LY3832479 1400 mg. Part 3 is not powered for inference between the two treatment arms.

If enrolling to a placebo-controlled trial is challenged by an effective medication becoming available for prevention of COVID-19 and SARS-CoV-2, then the placebo arm may be dropped.

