9.4.6. Secondary Endpoints

As key secondary analyses, the proportion of participants who experience each of the following will be assessed on the Prevention population:

- Cumulative incidence of moderate or worse severity COVID-19 (within 8 weeks from randomization)
- Cumulative incidence of SARS-CoV-2 infection (within 4 weeks from randomization)

The analysis model for the key secondary analyses will be similar to the primary analysis model. To control for multiplicity, a fixed-sequence approach will be used to test the primary and key secondary endpoints. A separate testing sequence will be used for each part of the study. The final testing sequences will be specified in the SAP.

Additionally, the following secondary analyses will be conducted on the Prevention population:

- The proportion of participants who experience each of the following will be compared across treatments:
 - Cumulative incidence of SARS-CoV-2 infection, up to 8 weeks from randomization
 - Hospitalization or death due to COVID-19, up to 8 weeks from randomization
 - Hospitalization due to COVID-19, COVID-19 related emergency visit, or death
 - Death due to COVID-19, up to 8 weeks from randomization

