#### Overall Rationale for the revision on Version 3:

The sponsor is adding Part 3 of Study PYAD. The SAP is being updated to reflect the changes implemented in protocol amendment (c).

Part 3 of the study is a two arm, outpatient, open label, exploratory cohort evaluating the efficacy and safety of LY3819253 and LY3819253 in combination with LY3832479 in participants positive for SARS-CoV-2 with or without symptoms in staff and residents who are at higher risk for more severe disease and hospitalization in skilled nursing and assisted living facilities.

Section # and Name	Description of Change	Brief Rationale
Throughout	PYAD(b) changed to PYAD(c)	Protocol Update – amendment (c).
Section 4.3 – Exploratory Endpoints	Exploratory Objectives for Part 3 added	Protocol Update – amendment (c).
5.1 – Summary of Study Design	Schema for Part 3 added.	Protocol Update – amendment (c).
5.1.1 – Screening Period	Screening period information for Part 3 added.	Protocol Update – amendment (c).
5.1.2 – Evaluation Period	Evaluation period information for Part 3 added.	Protocol Update – amendment (c).
5.1.3 – Follow-up Period	Follow-up period information for Part 3 added.	Protocol Update – amendment (c).
5.2 – Determination of Sample Size	Language discussing sample size for Part 3 added	Protocol Update – amendment (c).
5.3.2 Blinding	Added open-label language regarding Part 3	Protocol Update – amendment (c).
6.1.1 – Analysis Populations	Added Safety and Treatment populations for Part 3.	Protocol Update – amendment (c).
6.1.4 – Analysis Methods	Elaborated that only Parts 1 and 2 of the study will be controlled for multiplicity.	Protocol Update – amendment (c).

Section # and Name	Description of Change	Brief Rationale
6.10.3.5 - COVID-19-Related Deterioration (Hospitalization, Emergency Room, or Death by Day 57)	Elaborated that death also needed to be related to COVID-19 to satisfy the endpoint.	Clarification
6.16.1.3 – SARS-CoV-2 Clearance	Part 3 analysis added to description	Protocol Update – amendment (c).
6.16.2.7 – Persistently High Viral Load	Exploratory endpoint added	Protocol Update – amendment (c).

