Characterize clinical status for participants.	
Proportion (percentage) of participants who experience these events:
 
 
COVID-19 related hospitalization (defined as <math>\geq 24</math> hours of acute care),
 
COVID-19 related emergency room visit, or
 
death
 

Characterize COVID-19 illness and severity according to NIAID ordinal scale(s)	
 
Worst score on a NIAID ordinal scale(s)
 

Evaluate the mortality due to COVID-19	
 
Proportion of participants who die due to COVID-19.
 

Characterize SARS-CoV-2 viral endpoints.	
 
Proportion of participants that achieve SARS-CoV-2 clearance within 8 or 29 days of baseline.
 
Time to SARS-CoV-2 clearance.
 

Characterize emergence of viral resistance to LY3819253 or LY3832479	
 
Comparison from baseline to at least the last positive sample in a subset of participants.
 

Evaluate the duration of hospitalization due to COVID-19	
 
Cumulative days of hospitalization in those who are hospitalized due to COVID-19.
 

Abbreviations: COVID-19 = coronavirus disease – 2019; NIAID = National Institute of Allergy and Infectious Diseases; RT-PCR = reverse transcription – polymerase chain reaction; SARS-CoV-2 = severe acute respiratory syndrome coronavirus 2.

a as defined in Table 1 of the protocol

**Table PYAD.4.6. Exploratory Objectives of Part 3 of Study J2X-MC-PYAD(c) in Participants Positive at Baseline for SARS-CoV-2 RT-PCR and Negative at Baseline for Serology**

[figure not shown]
Objectives	Endpoints
Exploratory	
Compare the frequency of hospitalization due to COVID-19	
 
Proportion of participants who are hospitalized or experience death due to COVID-19
 

Characterize clinical status for participants.	
Proportion (percentage) of participants who experience these events:
 
 
COVID-19 related hospitalization (defined as <math>\geq 24</math> hours of acute care),
 
COVID-19 related emergency room visit, or
 
Death due to COVID-19
 

Characterize COVID-19 illness and severity according to NIAID ordinal scale(s)	
 
Worst score on a NIAID ordinal scale(s)
 

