#### **6.16.2.6. All Cause Mortality**

The proportion of patients that experience death after randomization will be summarized by treatment in frequency tables and listed for participants in the Safety Populations.

Additionally, at the End of Evaluation Database Lock, the number of patients who experienced death anytime after randomization will be analyzed to compare each study intervention versus placebo in the Prevention and Treatment populations, if there are sufficient data available. In addition, the number of patients that experience death after randomization will be analyzed using logistic regression to compare each study intervention versus placebo at each dose level, if there are sufficient data available.

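### SAP 6.10.3.5 counts only COVID-19-related deaths in the Part 1 clinical-status composite, whereas the protocol and the SAP's own Table PYAD.4.1 count death without qualification.

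*SAP*

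**What the plan says.** **Protocol.** The synopsis and Section 3 list the composite among the Part 1 other secondary endpoints, under the objective of characterizing clinical status. The hospitalization and emergency-visit components are tied to COVID-19; the last component is not: "COVID-19 related emergency room visit, or ○ death". Section 9.4.6 repeats this as "Hospitalization due to COVID-19, COVID-19 related emergency visit, or death". A separate mortality endpoint is cause-specific: "Proportion of participants who die due to COVID-19 (according to the investigator".

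**SAP objectives tables.** Table PYAD.4.1 (Part 1 secondary) and Tables PYAD.4.4 and PYAD.4.5 (exploratory, Part 1 and Part 2 treatment populations) leave death unqualified. Table PYAD.4.6 (Part 3) uses "death due to COVID-19".

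**SAP analysis section.** Section 6.10.3.5 defines deterioration by Day 57 with "death related to COVID-19" as its third component. It uses logistic regression if data suffice, with non-responder imputation (NRI) for missing data. The same analysis is repeated in the treatment populations.

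**SAP revision table.** The entry for 6.10.3.5 reads "Elaborated that death also needed to be related to COVID-19 to satisfy the endpoint". Its rationale column holds one word, clarification.

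**The concern.** Restricting a component of a composite changes which participants have an event, so it changes the endpoint. A reader who takes the endpoint from the protocol or Table PYAD.4.1 would expect any death to count, but the analysis section would produce something else under the same objective.

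The difference is not trivial in kind. Many participants are residents of skilled nursing and assisted living facilities, where deaths from other causes are to be expected. The protocol leaves attribution of COVID-19 death to the investigator in its mortality endpoint, and SAP 6.10.3.5 names no adjudication or rule for relatedness. With the restriction, the composite is also close to the endpoint in SAP 6.10.3.4 (hospitalization or death due to COVID-19), with emergency visits added. What is at stake is whether the protocol's stated secondary endpoint is reported at all, and whether readers can tell which version they are seeing.

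**Working it through.** The documents state no event rate, power or sample size for this composite, so there is no plan figure to reproduce. The check is a comparison of current texts, followed by one illustration on assumed rates.

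**1. Where death is qualified**

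| Place | Death component |
|---|---|
| Protocol synopsis and Section 3, Part 1 | unqualified |
| Protocol 9.4.6 | unqualified |
| SAP Tables PYAD.4.1, 4.4, 4.5 | unqualified |
| SAP Table PYAD.4.6 (Part 3) | COVID-19 only |
| SAP 6.10.3.5 | COVID-19 only |

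**2. Is the unqualified wording loose shorthand?** Probably not. In Protocol 9.4.6 the neighbouring items attach COVID-19 to death where cause-specific death is meant, and the composite does not.

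**3. Did the protocol follow the SAP?** No. SAP version 4 is dated 7 December 2020. The current protocol cites data as of 31 December 2020 in Section 2.3, so it is later, and it still leaves death unqualified. The conflict is between current texts, not only with a change log.

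**4. Who is affected?** Only participants who die by Day 57 of a cause not attributed to COVID-19 and who had no earlier COVID-19 hospitalization or emergency visit. Anyone with such an earlier event counts under both definitions.

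**5. How does the SAP then treat them?** Unclear. Section 6.3.3 makes a participant a non-responder if the efficacy criterion is not met or data are missing, and treats an inadequately assessed participant as having failed treatment. For an endpoint where meeting the criterion is the bad outcome, this could be read either way for someone who died before Day 57. The rule in 6.3.2 that treats unrelated death as no event belongs to a supplementary analysis of the COVID-19 primary and key secondary endpoints, not to this composite.

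**6. Illustration that the two versions can differ.** Inputs: 650 per arm (half of the approximately 1300 in the Part 1 sample-size section); risk ratio 0.33 (the protocol's assumption for the primary and key secondary endpoints, borrowed here); an assumed placebo rate *p* of COVID-19-related composite events; an assumed rate *u* of unrelated death, equal in both arms and independent of COVID-19 events. Neither *p* nor *u* is in the documents.

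- Any-death rate, placebo: *p* + *u* − *pu*
- Any-death rate, active: 0.33*p* + *u* − 0.33*pu*

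For *p* = 2%, *u* = 1%: placebo 0.02 + 0.01 − 0.0002 = 0.0298; active 0.0066 + 0.01 − 0.000066 = 0.0165; ratio about 0.56.

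Risk ratio of the any-death composite, with approximate power from a two-proportion comparison in brackets:

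| *p* | *u* = 0 | *u* = 0.5% | *u* = 1% | *u* = 2% |
|---|---|---|---|---|
| 2% | 0.33 (56%) | 0.47 (44%) | 0.56 (36%) | 0.67 (26%) |
| 4% | 0.33 (85%) | 0.41 (79%) | 0.47 (73%) | 0.56 (62%) |

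The column *u* = 0 corresponds to the COVID-19-death version, if attribution is perfect and unrelated deaths count as no event.

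**The case against.** **The change is disclosed and may be permitted.** This stands in part. The restriction is openly listed. Protocol 9.4 requires an amendment only for a change to a principal feature; other changes to analysis methods, with their justification, "will be described in the statistical analysis plan (SAP) and the clinical study report (CSR". But one word is not a justification for changing an endpoint component, and the objectives tables were left as they were.

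**Other-cause deaths are reported elsewhere.** This stands. SAP 6.16.2.6 says "The proportion of patients that experience death after randomization will be summarized by treatment", with treatment comparisons if data suffice. Deaths also receive narratives. No death disappears from the report, but the protocol's composite does.

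**A cause-specific composite suits a COVID-19 antibody.** This is a reasonable preference, and the illustration shows the price of the alternative: unrelated deaths dilute the ratio and reduce power. It is why the any-death version need not be the only one reported. Attribution is not new either, since the protocol already requires it for the other two components.

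**Stronger readings that the documents do not support.**

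- A reader might infer that the definition was changed after Part 1 was unblinded, because the SAP says version 3 preceded unblinding and says of version 4 only that it preceded the first Part 3 visit. That is silence, not evidence; no Part 1 lock date is given.
- A reader might infer that every death not attributed to COVID-19 becomes a non-event. Steps 4 and 5 of the working show otherwise.
- A reader might infer that the number affected rivals the expected composite events. No expected count or background mortality is stated.

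**Conclusion.** The inconsistency is real. As written, SAP 6.10.3.5 does not analyse the composite that the protocol and SAP Table PYAD.4.1 define, and no reason is given for the difference. The number of participants affected cannot be derived from the documents. The illustration shows only that, on assumed rates, the two versions could give visibly different estimates.

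The weight is low. This is an other secondary endpoint in Part 1, outside the multiplicity scheme in SAP 6.5, and its testing is conditional on sufficient data. Primary and key secondary conclusions do not depend on it. The conclusion rests on reading unqualified death as any death, which the contrast with the neighbouring cause-specific endpoints supports.

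**What to change.** In SAP 6.10.3.5, report two versions side by side: COVID-19 hospitalization, COVID-19 emergency visit or any death; and the same with COVID-19-related death only. Label which one is the protocol-defined endpoint. Align Tables PYAD.4.1, 4.4 and 4.5 with the text of 6.10.3.5, and check Table PYAD.4.6 against the same decision, because the treatment table in Protocol Section 3 that covers Part 3 also leaves death unqualified. State explicitly how a death not attributed to COVID-19 is coded in the narrower version, so that NRI is not left to interpretation.

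If the sponsor wants the narrower version as the main one, it should align the protocol wording and give the reason.

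The cost is SAP wording and one extra table. The downside is that unrelated deaths dilute the any-death estimate, which is a reason to show both versions.

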### 6.11. Pharmacokinetic and Pharmacokinetic/Pharmacodynamic Methods

Pharmacokinetic (PK), pharmacodynamic (PD) and PK/PD analyses are the responsibility of Eli Lilly and Company PK/PD group.

A summary of LY3819253 and LY3832479 concentration-time data will be reported in the clinical study report. Population PK model-based analyses, exploratory exposure-response analyses (a.k.a., population PK/PD modeling) of safety, pharmacology and efficacy, and any alternative approaches to efficacy analysis (including viral load definition in Section 6.16.2.1) may be performed.

